#### **Efficacy outcome measures related to participant infectivity:**

The prevalence of infectiousness (i.e. the proportion of individuals infecting at least one mosquito) will be presented per arm and timepoint and presented for DMFA and DSF separately. We will fit a logistic regression with fixed factors time and study arm and their interaction to estimate proportions (or adjusted proportions if baseline proportions differ quite significantly between arms) at each timepoint for each arm and compare prevalence estimates between time-points for each arm and between arms for each time-point using odds ratios (and 95% CIs).

Similar to the paragraph on oocyst prevalence, naturally acquired transmission reducing immunity and human genetic factors may be added as fixed effect in logistic regression models on participant infectivity as binary dependent variable.

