### Efficacy outcome measures

#### **Efficacy outcome measures related to within-group % reduction in proportion infected mosquitoes:**

We will determine averaged within-individual percent reduction in the proportion of mosquitoes infected at days post-treatment (1, 5, 14) compared to baseline (day 0) for each group. This will be assessed through DMFA and DSF and outcomes for these different feeding assays will be presented separately as percentage reduction (with 100% as total reduction of transmission, and negative values as enhanced transmission) with 95% confidence interval. Data will be analysed for all individuals who received the product per protocol and only for those individuals who are infectious at baseline (i.e. infecting at least one mosquito with any number of oocysts). All analyses on within-individual percentage reduction in the proportion of infected mosquitoes will use a mixed effects generalized linear model assuming a binomial error structure and a log-link, using individual mosquito data with day of follow-up and dose of TB31F and their interaction as fixed effects. A random intercept will be added to models to allow for participant-level variation in pre-intervention transmissibility and thus account for the correlation between outcomes for mosquito samples from the same participant (i.e. intra-cluster correlation).

In exploratory analyses, these analyses will be performed following stratification for naturally acquired transmission reducing immunity, as quantified by SMFA at baseline (pre-TB31F administration) samples.

The impact of naturally acquired transmission reducing immunity, assessed in baseline samples by SMFA (TRA>50%; TRA>80%) and by antibody prevalence to known gamete antigens Pfs230 and Pfs48/45, on infecting mosquitoes will also be determined. For this, TRA as categorical variable and antibody prevalence (binary variable), will be added as fixed effects to mixed effects logistic regression models on proportion infected mosquitoes at baseline (pre-TB31F administration). These models may be expanded to include human genetic factors (e.g. a fixed effect for HbAS or HbAC carriage as compared to wild-type HbAA).

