#### **Efficacy outcome measures related to mosquito infection prevalence (oocyst prevalence):**

In this analysis, we do not assess reductions in infection rates but present the average prevalence of infected mosquitoes (percentage of mosquitoes with any oocyst density) at each timepoint for each arm. Data will be presented for DMFA and DSF separately.

If, despite randomization, there are considerable differences in baseline infectivity, we may adjust for baseline infectivity. We will fit a mixed effects logistic regression with fixed factors time and study arm and their interaction and individual-specific random intercepts to estimate proportions (or adjusted proportions) at each timepoint for each arm and compare prevalence estimates between time-points for each arm and between arms for each time-point using odds ratios (and 95% CIs).

In exploratory analyses, these analyses will be performed following stratification for naturally acquired transmission reducing immunity, as quantified by SMFA at baseline (pre-TB31F administration) samples.

The impact of naturally acquired transmission reducing immunity, assessed in baseline samples by SMFA (TRA>50%; TRA>80%) and by antibody prevalence to known gametocyte antigens Pfs230 and Pfs48/45, on oocyst prevalence will also be determined. For this, TRA as categorical variable and antibody prevalence (binary variable), will be added as fixed effects to mixed effects logistic regression models on mosquito infection prevalence at baseline (pre-TB31F administration). These models may be expanded to include human genetic factors (e.g. a fixed effect for HbAS or HbAC carriage as compared to wild-type HbAA).

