#### **Efficacy outcome measures related to mosquito infection intensity (oocyst density):**

In this analysis, we do not assess reductions in infection intensity but present the average oocyst density at each timepoint for each arm. Data will be presented for DMFA and DSF separately.

We will fit a mixed effects negative binomial regression model with fixed factors time and study arm and their interaction and individual-specific random intercepts to estimate average oocyst densities at each timepoint for each arm and compare prevalence estimates between time-points for each arm and between arms for each time-point using oocyst density ratios (and 95% CIs).

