#### **Efficacy outcome measures related to transmission reducing activity (reductions in oocyst intensity):**

We will determine averaged within-individual percent reduction in the density of oocysts at days post-treatment (1, 5, 14) compared to baseline (day 0) for each group. This will be assessed through DMFA, DSF and SMFA and outcomes for these different feeding assays will be presented separately as percentage reduction (with 100% as total reduction of transmission, and negative values as enhanced transmission) with 95% confidence interval. For DMFA and DSF, these data will be analysed for all individuals who received the product per protocol without restrictions to baseline infectivity, and for those individuals who are infectious at baseline (i.e. infecting at least one mosquito with any number of oocysts). For SMFA, these data will be analysed for all individuals who received the product per protocol without restrictions to baseline infectivity in DMFA or DSF, as well as for the subset of individuals who are infectious at baseline. SMFA, an exploratory outcome, will be conducted after unblinding to allow testing of a realistic sub selection of test and control samples. Participants may have naturally acquired TRA due to exposure to gametocytes prior to enrollment; SMFA on baseline samples will allow us to identify these individuals. Additional samples that are most informative for determining the IC80 will be selected based on the ELISA data and tested in the SMFA. For this, one person not involved in data analysis will be unblinded and select samples based on ELISA values and treatment arm.

All analyses on within-individual percentage reduction in oocyst density will use a mixed effects negative binomial regression model with day of follow-up and dose of TB31F as fixed effects. A random intercept will be added to models to allow for participant-level variations (i.e. intra-cluster correlation).

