### Outcome measures related to the correlation between transmission assays:

The association between DMFA and DSF will be analysed across common timepoints for the two outcomes: (1) whether or not an individual is infectious and (2) the proportion of infected mosquitoes. A mixed effects logistic regression with logit-link will be used to express the association for (1) using the risk ratio. For (2) a mixed effects linear model will be used and the association will be expressed in terms of the slope. We use individual-specific random intercepts in both models to account for the within-individual correlation.

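### The participant-infectivity model ignores repeated feeds on the same person, so its within-arm intervals are too wide; separately, baseline adjustment hangs on an undefined imbalance (both low weight)

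*SAP*

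**What the plan says.** **Participant infectivity.** Outcomes 17-18 record whether a participant infects any mosquito, by DSF on days 0, 1 and 5 and by DMFA on days 0, 1, 5 and 14. In the section on analyses in relation to endpoints the SAP says: "We will fit a logistic regression with fixed factors time and study arm and their interaction to estimate proportions". The same model serves two kinds of comparison: between timepoints within an arm, and between arms at a timepoint. No random effect, GEE or robust variance is named. The later remark that the section resembles the one on oocyst prevalence concerns only immunity and genetic covariates, so it does not bring in that section's random intercept.

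**Elsewhere.** The percent-reduction section says "A random intercept will be added to models to allow for participant-level variation in pre-intervention transmissibility". Oocyst prevalence has "fixed factors time and study arm and their interaction and individual-specific random intercepts to estimate proportions", and oocyst density a "mixed effects negative binomial regression model with fixed factors time and study arm and their interaction and individual-specific random intercepts". The transmission-reducing-activity section also adds a random intercept. In the assay-correlation section, where infectious yes/no is one of the two outcomes, the SAP says "We use individual-specific random intercepts in both models to account for the within-individual correlation".

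**Baseline adjustment.** Oocyst prevalence: "If, despite randomization, there are considerable differences in baseline infectivity, we may adjust for baseline infectivity". Participant infectivity: "adjusted proportions if baseline proportions differ quite significantly between arms". Neither gives a threshold, a test or the form of the covariate.

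**The concern.** (a) Ordinary logistic regression treats the day-0 and day-5 feeds of one person as if they came from two people. A difference between two positively correlated proportions varies less than that model assumes, so its intervals for change from baseline are too wide. The SAP recognises this correlation for the same variable in another section, so the omission looks like an oversight.

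(b) When adjustment depends on an undefined imbalance, two odds ratios exist for one prespecified comparison, and which is reported is settled after the data are seen. If the choice falls on no adjustment, the precision that the day-0 feed could give is lost. Day 0 is also already a level of the time factor, so the SAP leaves unclear how baseline would enter as a covariate as well.

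**Working it through.** **Part (a): inputs.** From the SAP's sample-size section: 30 per arm, 40 mosquitoes per feed, 15% of mosquitoes infected, intra-cluster correlation 0.5, and 66.0-79.5% of people infectious at enrolment. Assumed, because the SAP does not give them: the ICC is on the latent logistic scale, and the between-day correlation r of a participant's log-odds infectivity is 1, 0.8, 0.5 or 0.25.

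*Step 1, check the assumed scale.* Latent ICC = s²/(s² + π²/3) = 0.5 gives s² = 3.29. With 15% of mosquitoes infected on average, the chance that at least one of 40 is infected, averaged over participants, is 77%. This lies inside the SAP's 66.0-79.5%.

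*Step 2, large-sample ratio.* Let φ be the correlation between a person's day-0 and later yes/no results. With equal prevalence p on both days, the model as written has Var = 2/(np(1−p)), and the true variance is that times (1−φ). The stated SE is therefore 1/√(1−φ) times the true SE.

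| r | 1 | 0.8 | 0.5 | 0.25 |
|---|---|---|---|---|
| φ | 0.50 | 0.37 | 0.21 | 0.10 |
| SE ratio | 1.41 | 1.26 | 1.13 | 1.05 |

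For example, 1/√(1−0.50) = 1.41.

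*Step 3, n = 30, 40,000 simulated arms with no change.* The empirical SD of the within-arm log odds ratio is 0.477 / 0.537 / 0.601 / 0.635, against a mean model SE of about 0.64. The nominal 5% Wald test rejects about 0.3% / 1.0% / 2.0% / 2.7%. The fair benchmark is not 5%: with truly independent feeds this test rejects about 3.7% at n = 30, because of small numbers and discreteness. Only the shortfall below that figure is due to the missing clustering.

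*Step 4, sensitivity.* With a participant variance of 0.5 the ratios fall to 1.08 / 1.05 / 1.03 / 1.01. That variance, however, implies 97% infectious at day 0, outside the SAP's range.

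*Step 5, power of the within-arm test.* At a 90% reduction, power is about 99% or more with or without clustering. At a 50% reduction it is about 21% / 23% / 25% / 26% as written and 47% / 40% / 33% / 30% with clustering.

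*Step 6, between arms at one timepoint.* Each participant contributes one feed, and the time-by-arm model is saturated. In a simulated three-arm, four-timepoint data set, the day-5 SE for 100 mg against control was 0.5634 with and without clustering.

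**Part (b): how often arms differ by chance at day 0.** Exact binomial, same true proportion in both arms, 66.0% to 79.5% infectious:

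| Gap | 30 vs 30 | 15 vs 30 |
|---|---|---|
| at least 10 points | 50% to 42% | 58% to 51% |
| at least 20 points | 13% to 8% | 22% to 15% |

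The first column pools the two control groups of Table 3 (15 + 15); the second compares a dose arm with its own 15 controls. If the trigger were p < 0.05 at day 0, it would fire in about 5% of trials.

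*One concrete rule tried.* Adjust only if day-0 p < 0.05; latent correlation 0.6; 73% infectious at day 0 and 68% at day 5; 2,000 null trials. Type I error was 3.65% never adjusting, 3.7% always adjusting and 3.4% with the conditional rule (simulation error about 0.4 points).

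**The case against.** The other side has a good case on weight. Part (a) makes the analysis conservative, touches only within-arm contrasts of secondary outcomes that the SAP itself calls hypothesis-generating, and changes nothing at the effect the trial expects. For mosquito infection, outcomes 9-10 already compare baseline-relative reductions between groups, so the oocyst-prevalence odds ratios are not the only between-arm evidence. All of this stands. It limits the importance but does not make the model right, and outcomes 9-10 do not cover participant infectivity.

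Three stronger readings are tempting, and the SAP does not support them:

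- *That missing clustering creates false positives.* It does the reverse within arms and has no effect between arms at one timepoint.
- *That conditional adjustment inflates type I error.* The SAP's trigger is imbalance at baseline, not the post-baseline result. It does not say that the more favourable analysis will be reported, and the one rule tried showed no inflation.
- *That adjustment would be triggered in about half of trials.* This holds only if 10 points, or 3 people in 30, counts as considerable. Stricter readings bring it down to 8-13% or about 5%.

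Citing the other sections shows that the SAP is inconsistent about clustering. It does not show that a single random intercept is adequate there; that is a separate question, not examined here.

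**Conclusion.** Both parts hold, at low weight.

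(a) The model is wrong as written for comparisons with day 0. The within-arm SE is overstated by a factor of about 1.05 to 1.41 in large samples. This rests on assumed between-day correlations of 0.25 to 1 and on reading the ICC of 0.5 as latent; a lower participant variance makes it smaller. The cost is precision when reductions are moderate.

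(b) The adjustment rule is not a rule. A chance gap that some analysts would call considerable is common, and one that most would call considerable is not rare. What is lost is prespecification and some precision; error control has not been shown to fail.

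**What to change.** **Participant infectivity.** Keep the time-by-arm logistic model, but fit it by GEE or with standard errors clustered on participant. The odds ratios then stay population-averaged, in line with the proportions reported; a random intercept would make them participant-specific. A sentence on what is reported if no one in a cell is infectious would help under either model.

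**Oocyst prevalence and participant infectivity, between arms.** Delete both conditional clauses. State that every post-baseline between-arm comparison includes the participant's day-0 infectivity in the same assay as a covariate, whatever the imbalance, and name its form (for example the empirical logit of the proportion of mosquitoes infected). Only post-baseline feeds should be outcomes in that model, so that day 0 is not both a response and a covariate.

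**Cost.** A few sentences in the SAP and no new data, since the day-0 feeds are already planned. The small downside is that the adjusted odds ratio is conditional on baseline and comes from a different model than the day-0 comparisons, so it must be labelled as such. Fixing the rule as never adjusting would also remove the discretion, with less precision.

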#### **Efficacy outcome measures related to mosquito infection intensity (oocyst density):**

In this analysis, we do not assess reductions in infection intensity but present the average oocyst density at each timepoint for each arm. Data will be presented for DMFA and DSF separately.

We will fit a mixed effects negative binomial regression model with fixed factors time and study arm and their interaction and individual-specific random intercepts to estimate average oocyst densities at each timepoint for each arm and compare prevalence estimates between time-points for each arm and between arms for each time-point using oocyst density ratios (and 95% CIs).

#### **Efficacy outcome measures related to transmission reducing activity (reductions in oocyst intensity):**

We will determine averaged within-individual percent reduction in the density of oocysts at days post-treatment (1, 5, 14) compared to baseline (day 0) for each group. This will be assessed through DMFA, DSF and SMFA and outcomes for these different feeding assays will be presented separately as percentage reduction (with 100% as total reduction of transmission, and negative values as enhanced transmission) with 95% confidence interval. For DMFA and DSF, these data will be analysed for all individuals who received the product per protocol without restrictions to baseline infectivity, and for those individuals who are infectious at baseline (i.e. infecting at least one mosquito with any number of oocysts). For SMFA, these data will be analysed for all individuals who received the product per protocol without restrictions to baseline infectivity in DMFA or DSF, as well as for the subset of individuals who are infectious at baseline. SMFA, an exploratory outcome, will be conducted after unblinding to allow testing of a realistic sub selection of test and control samples. Participants may have naturally acquired TRA due to exposure to gametocytes prior to enrollment; SMFA on baseline samples will allow us to identify these individuals. Additional samples that are most informative for determining the IC80 will be selected based on the ELISA data and tested in the SMFA. For this, one person not involved in data analysis will be unblinded and select samples based on ELISA values and treatment arm.

All analyses on within-individual percentage reduction in oocyst density will use a mixed effects negative binomial regression model with day of follow-up and dose of TB31F as fixed effects. A random intercept will be added to models to allow for participant-level variations (i.e. intra-cluster correlation).

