#### Secondary efficacy objectives

- To assess the transmission-blocking activity of mAb TB31F assessed in the Direct Skin Feed (DSF) and DMFA at each dose level in naturally *P. falciparum* infected individuals
- To assess mosquito infection rate as measured by the proportion of dissected mosquitoes with any number of oocysts at each dose level in naturally *P. falciparum* infected individuals
- To assess the intensity of mosquito infection as measured by the average number of oocysts in dissected mosquitoes at each dose level in naturally *P. falciparum* infected individuals
- To assess participant infectivity after mAb TB31F administration at each dose level in naturally *P. falciparum* infected individuals

- To assess the transmission-reducing activity of participant serum after TB31F administration as assessed in the Standard Membrane Feeding Assay (SMFA) at each dose level in naturally *P. falciparum* infected adults and children

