#### Exploratory objectives

- To develop an integral pharmacokinetic/pharmacodynamic (PK/PD) model describing the relationship between TB31F dose, time, individual characteristics, serum TB31F concentrations and SMFA and DSF/DMFA
- To assess the transmission-blocking activity of participant serum after TB31F administration as assessed in the Standard Membrane Feeding Assay (SMFA) at each dose level in Malian individuals
- To assess the quantitative relationship between SMFA, DSF, and DMFA results
- To assess the IC80 serum concentration after TB31F administration resulting in 80% transmission-blocking activity (TBA) in naturally *P. falciparum* infected individuals
- To assess the IC80 serum concentration after TB31F administration resulting in 80% transmission-reducing activity (TRA) in naturally *P. falciparum* infected individuals
- To assess the impact of naturally acquired TRA, present prior to TB31F administration, on transmission endpoints and TB31F efficacy estimates
- To assess human and parasite genomic variation and association with parasite measures
- To assess the impact of plasma biomarkers on malaria transmission efficiency

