Modeled TRA and TBA estimates (based on antibody concentration) will be plotted against observed estimates and may be used to determine the duration of TB31F activity at time-points when no feeding assays were performed. This will be achieved by analysing pharmacokinetic and pharmacodynamic data by means of non-linear mixed effects modeling. We will fit single and multicompartmental methods to the obtained pharmacokinetic data and investigate both linear and non-linear elimination and disposition. Thereafter, we will investigate whether the pharmacokinetics relate with TBA/TRA. The developed pharmacokinetic-pharmacodynamic model will be used for *in silico* exploration of:

- TB31F dosing regimens needed to achieve at least 80% TRA during an epidemiological relevant time frame (e.g. a typical transmission season of three months)
- the effect of monoclonal antibody engineering, resulting in a longer circulation half-life due to a more favorable pH-dependent binding to human neonatal receptor, on the dose needed to achieve at least 80% TRA during an epidemiological relevant time frame (e.g. a typical transmission season of three months)

We may calculate the percentage of individuals per group that have at least 50%, 80% and 90% TRA per timepoint and per study arm and the percentage of individuals with statistically significant TRA at each timepoint. Mean TRA levels may also be calculated per study group per timepoint and compared between groups.

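### By-dose SMFA transmission-reducing activity is a secondary objective, but its post-baseline samples are chosen for the IC80 by ELISA value and arm under an unstated rule, so raw group summaries can be biased

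*SAP*

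**What the plan says.** **Rank.** Under Cohort 2, Secondary efficacy objectives, the SAP lists "To assess the transmission-reducing activity of participant serum after TB31F administration as assessed in the Standard Membrane Feeding Assay (SMFA) at each dose level". The SMFA item under Exploratory objectives is a different measure: "To assess the transmission-blocking activity of participant serum after TB31F administration as assessed in the Standard Membrane Feeding Assay (SMFA"). In Analysis Methods, the section on transmission reducing activity calls the whole assay exploratory: "SMFA, an exploratory outcome, will be conducted after unblinding to allow testing of a realistic sub selection of test and control samples".

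**Selection.** Baseline samples are tested to find participants with naturally acquired TRA. For the rest, "Additional samples that are most informative for determining the IC80 will be selected based on the ELISA data and tested in the SMFA", and "one person not involved in data analysis will be unblinded and select samples based on ELISA values and treatment arm". No rule, number per arm or day, or weighting is given.

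**Use.** Outcome 20 is the percent reduction in oocyst intensity against experimental controls, which is how the section on inhibitory concentrations defines TRA in the SMFA. It is to be compared within and between groups at days 0, 5, 14, 28, 56 and 84. Outcome 21 does the same for transmission-blocking activity (TBA). The analysis section promises a percent reduction per group with a 95% confidence interval, from a negative binomial model with day and dose as fixed effects and a random intercept. The inhibitory-concentration section adds the percentage of individuals reaching 50%, 80% and 90% TRA, and "Mean TRA levels may also be calculated per study group per timepoint and compared between groups".

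**The concern.** Concentration is the path from dose to TRA. Picking samples on concentration therefore picks on the main determinant of the outcome, and picking on arm as well lets the selection differ between the groups being compared. The planned model has no concentration term and no selection weight, so it cannot undo this. The tested sera need not represent their arm on their day, and a dose contrast or a decline over time would then mix the drug's effect with the choice of samples.

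The rank matters too. If SMFA TRA by dose is secondary, a reader will take the group estimates as describing the randomised arms. If it is exploratory and serves the IC80, those estimates carry little weight. The SAP says both.

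**Working it through.** The SAP gives no figure to reproduce here. The powers under Sample size concern infected mosquitoes in DMFA and DSF and do not enter.

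**Inputs from the SAP**
- Curve: the IC80 formula makes the log oocyst ratio linear in the square root of concentration, with log(100/(100 − 80)) = log 5 = 1.609 at the IC80.
- 30 participants per TB31F arm, at doses of about 30 mg and 100 mg (Table 3).

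**Assumptions, not in the SAP**
- Intercept 0, so TRA(c) = 1 − exp(−1.609·√(c/IC80)).
- Lognormal concentrations with CV 40% or 80%; arm medians 0.1 to 10 times the IC80.
- Concentrations in the two arms in the ratio 100:30.
- One third of samples tested (10 of 30).

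Check of the formula: c = IC80 gives 1 − 1/5 = 80%; c = 0.3 × IC80 gives 1 − exp(−1.609 × 0.548) ≈ 58.6%, close to the simulated arm mean of 58.7%.

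**Step 1. Arm mean TRA (%) if the third nearest the IC80 is tested** (shifts taken before rounding)

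| Median / IC80 | CV 40%: all → tested (shift) | CV 80%: all → tested (shift) |
|---|---|---|
| 0.1 | 40.2 → 46.5 (+6.3) | 40.7 → 52.4 (+11.6) |
| 0.3 | 58.7 → 66.1 (+7.4) | 58.8 → 71.8 (+13.1) |
| 1 | 79.6 → 80.0 (+0.3) | 78.9 → 79.9 (+1.1) |
| 3 | 93.3 → 89.5 (−3.8) | 92.1 → 85.2 (−6.9) |
| 10 | 99.1 → 98.3 (−0.8) | 98.5 → 96.5 (−2.1) |

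Every arm moves toward 80%.

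**Step 2. Other rules.** Random selection shifts the arm mean by 0.0 points. Selection spread evenly over the ranked concentrations shifts it by −0.5 to +0.3.

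**Step 3. Contrast between arms (points), near-IC80 selection**

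| Lower arm median / IC80 | CV 40%: true → tested | CV 80%: true → tested |
|---|---|---|
| 0.3 | 21.0 → 13.9 | 20.1 → 8.1 |
| 0.55 | 18.6 → 6.5 | 17.8 → 2.6 |
| 1 | 14.5 → 10.7 | 14.2 → 6.5 |
| 3 | 5.8 → 8.8 | 6.4 → 11.3 |

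The first three rows shrink by 3.8 (14.5 − 10.7) to 15.2 (17.8 − 2.6). The last row grows by 3.0 and 4.9.

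**Step 4. Time course.** Suppose one third of an arm's samples is taken near the IC80 from days 5 to 84 together (CV 40%, starting median 3 × IC80, assumed half-life 30 days). The expected numbers tested at days 5, 14, 28, 56 and 84 are 2.5, 6.2, 15.0, 21.4 and 4.9. True mean TRA falls from 92.3% to 65.2% (27.1 points); the tested samples fall from 84.3% to 75.5% (8.8 points). With half-lives of 20 to 45 days and starting medians of 1 to 10 × IC80, most of the settings run leave at least one day with fewer than one expected sample.

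**Step 5. The IC80 itself.** Fitting the same regression to all samples and to near-IC80 samples only gives estimated/true IC80 of 0.997 and 1.000. Selecting on concentration does not distort it.

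**The case against.** A reader might infer that arm-level TRA will be biased toward 80%. The SAP does not support that. It says the samples are to be informative for the IC80, not that they lie near it. The IC80 comes from a fitted intercept and slope, and the IC50 is wanted too. A slope needs spread in concentration, so a range-spanning choice is at least as natural, and Step 2 shows that it does almost no harm. This stands: the bias is possible, not certain.

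A reader might also see a flat contradiction between the sub-selection and the clause "For SMFA, these data will be analysed for all individuals who received the product per protocol". That clause goes on to say that baseline infectivity in the other assays does not restrict the set, in contrast with the subset infectious at baseline. It mainly defines the population and need not promise that every serum is assayed. This stands too.

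The person who selects is outside the analysis, and nothing says that assay readers know the arm. That guards against analyst bias but does not make the sample representative.

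Finally, the SAP allows TRA inferred from antibody concentration, and the optional group summaries follow directly on the modelled estimates, so they may be meant as model-based. But inference from concentration is permitted only for some analyses and is not tied to the secondary objective. The per-group percent reduction with its confidence interval is described from assay data.

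The rest of the trial limits the stakes: the primary DMFA endpoint is untouched, secondary outcomes are called hypothesis-generating, and SMFA TBA is exploratory and is described as less informative than TRA.

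**Conclusion.** The point holds in limited form. The SAP gives SMFA TRA two ranks and draws post-baseline samples for one purpose, the IC80, while planning group summaries that need a representative set. Without a stated rule, raw group means, between-group contrasts and threshold percentages can be biased. If samples near the IC80 are chosen, arm means shift by up to about 13 points, and contrasts shrink by 4 to 15 points or grow by 3 to 5. If samples span the range, an arm mean moves by about half a point at most. These sizes rest on the assumed concentrations, variability, fraction tested and zero intercept, none of which the SAP states. The IC80 estimate is not put in doubt.

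**What to change.** 1. Give SMFA TRA the same rank in the objectives and in the analysis section.
2. Before unblinding, write down the selection rule and the number of sera per arm and day.
3. Flag ELISA-selected samples and use them only in the IC80 and PK/PD fit.
4. Base by-dose SMFA TRA (outcome 20, and outcome 21 as exploratory) on one named source: the fitted concentration-response model applied to every participant's ELISA concentrations; a complete or random set per arm and day; or selected samples weighted by known selection probabilities.
5. Align the SMFA days: the analysis section names days 1, 5 and 14, while outcomes 20 and 21 run from day 5 to day 84 after baseline.

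The model-based route needs no extra assays, because ELISA in the efficacy cohort is planned on every day that outcome 20 names. Its price is dependence on the fitted curve, and since participants may have natural TRA, the curve should allow for the baseline SMFA result. A random subset of the same total size also adds no assays but leaves somewhat fewer for IC80 enrichment. Otherwise the cost is SAP wording.
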